6.3. Other Endpoints

Baseline characteristics, including gender, race, ethnicity, alcohol and tobacco use, cardiovascular risk factors, primary diagnosis, time since primary diagnosis, and medical history will be collected prior to randomization. The collection of primary diagnosis and time since primary diagnosis was originally collected, but discontinued following a change to the CRF.

Concomitant and pre-study medications and non-drug treatments, including statins and non-statin lipid lowering treatments, will be collected throughout the study.

The date and time of each dose of study medication and the number of injections will be collected, as will reasons for discontinuation from study therapy and from the study. Treatment duration will be calculated as (the date of last active dose – the date of first active dose +15).

After the randomization visit, subjects will be directed to bring any used and unused syringe cartons to each visit. Used syringes will be returned to the study center in a biohazard container, when it is full, to receive a new container, and when directed by the study site.

Compliance is calculated as the percent of planned Investigational Product (IP) doses that were actually taken. Cartons lost prior to the administration of IP, or damaged and unused syringes, should not be counted as completed dose administrations. From this information, compliance, based on the dosing schedule, will be calculated as follows:

$$\text{Compliance} = 100\% \times \frac{\text{actual dose administrations}}{\text{dose administrations planned}}$$

- The number of actual dose administrations will be derived from the dosing CRF page.
- For subjects who do not have two dose adjustments, the number of dose administrations planned is one plus the integer part of one-fourteenth of the number of days from randomization to the date the site instructs the subject to discontinue study medication. For subjects who have two dose adjustments, the number of dose administrations planned is one plus the integer part of one-fourteenth of the number of days from randomization to the visit at which the second dose adjustment takes place plus one-twenty-eighth the number of days from the visit at which the second dose adjustment takes place to the date the site instructs the subject to discontinue study medication.
- In the event of an adverse event (AE) or reaction, subjects may be counseled to interrupt dosing permanently or temporarily. Doses not taken in such instances do not count as planned dose administrations and do not constitute lack of compliance.

6.3.1. Pharmacokinetic/Pharmacodynamic Endpoints

Pharmacokinetic/Pharmacodynamic (PK/PD) endpoints include plasma bococizumab concentration and PCSK9 concentration, however, samples will not be assayed for either.

Blood samples for bococizumab and PCSK9 will be collected as specified in the Schedule of Activities. On all bococizumab /PCSK9 blood sample collection days, samples must be collected prior to bococizumab dosing. After randomization, if lipid sampling has been postponed to an unscheduled visit, the corresponding ADA, PK, and PCSK9 samples should be postponed as well, and collected at the at the same time as the rescheduled lipid sample collection. Bococizumab/PCSK9 blood samples will be collected from all subjects, but only analyzed, if needed, to help understand the PK, PD, and safety response of bococizumab in this study population.

Baseline PCSK9 concentration will be defined as the mean of the last two non-missing values prior to and including randomization. If only one non-missing measurement is available, that measurement will serve as the baseline.

Samples for bococizumab and PCSK9, if analyzed, will be analyzed using a validated analytical method in compliance with Pfizer standard operating procedures.

6.3.2. Outcomes Research Endpoints

EuroQol 5-Dimensions (EQ-5D)

The EuroQol 5-Dimension (EQ-5D) is a generic measure of health-related quality of life. The EQ-5D is a subject completed instrument designed to assess impact on quality of life in five domains: mobility, self-care, usual activities, pain/discomfort, and anxiety/depression. Additionally, scores from the five domains may be used to calculate a single index value. The EuroQol EQ-5D Visual Analogue Scale (VAS) is a patient-completed 20 cm scale designed to rate an individual's current health state. The Health State Profile will be administered concurrently with the VAS-HEALTH STATE component of the EuroQol EQ-5D instrument.

The EQ-5D will be administered at Baseline and at Weeks 14, 26, 52, 104, 156, 208 and the subject's last visit (EDC or EOS). If the trial runs longer than 208 weeks, the EQ-5D will be collected every 52 weeks after Week 208.

The baseline values for the EQ-5D health index score and health state score will be the last non-missing value prior to or on the day of randomization.

The health index score will be calculated as per Shaw, Johnson and Coons (2005). Prior to calculating the health index score, the following are calculated

- I2 = number of item scores equal to 2
- I3 = number of item scores equal to 3

The health index score is calculated as follows:

1. The initial health index score is 1.0
2. If the mobility score
 - a. is 2, then 0.146016 is subtracted
 - b. is 3, then 0.557685 is subtracted
3. If the self-care score
 - a. is 2, then 0.1753425 is subtracted
 - b. is 3, then 0.4711896 is subtracted
4. If the usual activities score
 - a. is 2, then 0.1397295 is subtracted
 - b. is 3, then 0.3742594 is subtracted
5. If the pain/discomfort score
 - a. is 2, then 0.1728907 is subtracted
 - b. is 3, then 0.5371011 is subtracted
6. If the anxiety/depression score
 - a. is 2, then 0.156223 is subtracted
 - b. is 3, then 0.4501876 is subtracted
7. If $I2 + I3 > 1$, then $(I2 + I3 - 1)$ times 0.1395949 is added
8. If $I2 > 1$, then 0.0106868 times the square of $(I2 - 1)$ is subtracted
9. If $I3 > 1$, then 0.1215579 times $(I3 - 1)$ plus 0.0147963 times the square of $(I3 - 1)$ is added.

Health Care Resource Utilization (HCRU)

HCRU assessments will take place at each visit to collect data on the following:

- *The occurrence, overall length of stay, primary and secondary discharge diagnoses, duration of stay in different medical care units, and discharge disposition for all-cause hospitalizations;*

- *The occurrence, primary and secondary discharge diagnoses, overall length of stay, duration of stay in different medical care units, and discharge disposition for CV hospitalizations;*
- *The occurrence of emergency room visits;*
- *The occurrence of physician office visits;*
- *The occurrence of outpatient rehabilitation visits;*
- *The occurrence of all-cause hospitalizations within 30 days of a previous hospitalization, primary and secondary discharge diagnoses, length of stay, and discharge disposition;*
- *The occurrence of CV hospitalizations within 30 days of a previous hospitalization, primary and secondary discharge diagnoses, length of stay, and discharge disposition.*

The medical care units being assessed for these objectives include:

- *Cardiac Care Unit (CCU);*
- *Medical Intensive Care Unit (MICU);*
- *Neurology Intensive Care Unit (NICU);*
- *Surgical Intensive Care Unit (SICU);*
- *Thoracic Intensive Care Unit (TICU);*
- *Cardiac Step-down Unit;*
- *Pulmonary Step-down Unit;*
- *General ward;*
- *Dialysis Unit;*
- *Chemotherapy Unit;*
- *Infections disease isolation unit;*
- *Other.*

Discharge care disposition entities being evaluated for HCRU include:

- *Home self-care;*

- *Home health care;*
- *Nursing home care/skilled nursing facility;*
- *Rehabilitation facility;*
- *Hospice care;*
- *Death;*
- *And other potential disposition entities.*

6.4. Covariates

The randomization will be stratified by geographic region and LDL-C at the pre-screening visit (<100 mg/dL, ≥100 mg/dL). These variables will be included as stratification factors in log rank tests and Cox proportional hazards regression models and as covariates in linear models for efficacy endpoints. If the model fitting for the Cox proportional hazards model fails to converge, LDL-C at pre-screening will be removed as a stratification factor.

Geographic region and LDL-C pre-screening group will be obtained from the IRT system.

The geographic regions (5 levels) are:

- USA/Canada: Canada, Puerto Rico, United States of America.
- Latin America: Argentina, Brazil, Chile, Columbia, Mexico, Peru.
- Eastern Europe/Turkey: Czech Republic, Hungary, Poland, Romania, Russia, Slovakia, Turkey.
- Asia: China, India, Japan, Korea, Taiwan, Thailand.
- Rest of World: Australia, Belgium, Denmark, Finland, France, Germany, Ireland, Israel, Italy, Netherlands, New Zealand, Republic of South Africa, Spain, Sweden, Switzerland, United Kingdom.

If a subject changes investigational sites during the study, geographic region will be assigned according to the site at which the subject was randomized.

For all linear models that involve changes from baseline, the baseline value will also be used as a covariate.

7. HANDLING OF MISSING VALUES

For the clinical endpoints, not all subjects will have adjudicated and confirmed events. Subjects who do not experience any of the components of the primary endpoint will be censored on the date of last contact or 01November2016, whichever comes first. The date of last contact is defined as the date of death, if the date is not missing. Otherwise, the date of

last contact is defined as the study discontinuation date, the date of last visit, the date of last telephone contact, the onset date of the last AE, or the randomization date, whichever occurs last. The same censoring will be done for all other clinical endpoints and time to discontinuation from study. For analyses in the SAS, the date of first dose will be substituted for the randomization date.

Missing values for the Digit Span Forward, Digit Span Backward, Digit Symbol - Coding, Trail Making A and Trail Making B tests and the HVLT will not be imputed. For the Digit Span Forward and the Digit Span Backward, if the maximum number of digits is not reached and the last result is not a zero, the value will be missing.

Missing values for the PHQ-2 and PHQ-9 will not be imputed. If at least one item is missing, the total scores will be missing.

For all other efficacy and safety endpoints, missing values will not be imputed; missing values will remain missing.

For longitudinal analyses of circulating biomarker endpoints, a mixed model repeated measures (MMRM) model will be used for the analyses. As a likelihood method, MMRM models are valid when the data are missing at random (MAR). All subjects with a non-missing baseline value and at least one non-missing post-baseline value will be included in these analyses. Subjects with a missing baseline value will not contribute to the analyses. Consistent with MMRM model fitting, no explicit imputation of missing assessments will be performed.

Percent changes from baseline to last post-baseline value in LDL-C will be analyzed by analysis of covariance (ANCOVA). As a likelihood method, ANCOVA is valid when the data are MAR. Subjects with a non-missing baseline value and at least one non-missing post-baseline value will be included in the analyses. Subjects with a missing baseline value or without a non-missing post-baseline value will not contribute to the analyses.

When forming subgroups, subjects with a missing value on the classifying variable will not be included in a subgroup.

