#### **9.2.2.1.2. Other clinical secondary endpoints**

Other clinical secondary endpoints (as defined in [Appendix 4](#)) are the times from randomization to the first adjudicated and confirmed occurrence of:

- A composite endpoint of CV death, non-fatal MI, non-fatal stroke, and hospitalization for unstable angina;

- CV death;
- Any MI (fatal and non-fatal);
- Fatal MI;
- Non-fatal MI;
- Any stroke (fatal and non-fatal);
- Any stroke (fatal and non-fatal) of any etiology;
- Fatal stroke;
- Non-fatal stroke;
- Hospitalization for unstable angina;
- Hospitalization for congestive heart failure (CHF);
- Any coronary revascularization procedure;
- CABG;
- PCI;
- Any arterial revascularization;
- All-cause death.

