Once the conditions above are met to begin interim monitoring for benefit for a particular trial, a formal interim monitoring calculation will be performed for that trial for every DMC report, including safety reports not associated with DMC meetings. The analysis will be based on a log-rank test of all-cause death, from all data sources. Missing death dates will be imputed based on date of last contact.

When the test for all-cause death meets the above guideline for stopping a particular study early for overwhelming efficacy, the DMC will consider the all-cause death evidence within the context of all available efficacy and safety information in making their recommendation. In addition, the DMC may wish to give consideration to continuing the study, even where the all-cause death analysis meets the above criteria for benefit at an interim analysis, if the study is nearing completion (e.g., where 90% of targeted primary endpoint events have occurred).

The table below indicates the percent risk reduction associated with nominal p-values of 0.0003 and 0.0006 for various numbers of events, along with the probability of observing the reduction if the true risk reduction is 10%. Note that if the true risk reduction is 0% (no treatment effect) the probability of stopping is equal to the nominal p-value.

Table 1. Risk Reductions for Various Numbers of Events with Corresponding Probabilities

Number of Deaths	$\alpha = 0.0003$		$\alpha = 0.0006$	
	Percent Risk Reduction	Probability if 10% Risk Reduction	Percent Risk Reduction	Probability if 10% Risk Reduction
50	68.4%	0.07%	64.9%	0.16%
100	52.9%	0.11%	50.7%	0.20%
150	45.4%	0.14%	43.8%	0.24%
200	40.0%	0.22%	38.7%	0.34%
250	36.6%	0.27%	34.4%	0.57%
300	33.3%	0.42%	32.4%	0.59%
350	31.7%	0.43%	30.1%	0.78%
400	29.8%	0.55%	28.3%	0.95%

Analyses to Support the Regulatory Submission for the Treatment of Hyperlipidemia

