6. ENDPOINTS AND COVARIATES

6.1. Efficacy Endpoint(s)

This protocol will use an independent blinded Adjudication Committee wherein, to maintain scientific integrity, adjudication of disease-related efficacy endpoints will be performed. The Adjudication Committee will adjudicate potential disease-related endpoints, including CV deaths, all-cause death, MI, stroke, hospitalization for unstable angina needing urgent revascularization, hospitalization for unstable angina, hospitalization for CHF, and arterial revascularization procedures including percutaneous coronary interventions, CABG, and all other arterial revascularization procedures as described in [Appendix 1.2](#). The Adjudication Committee will confirm whether potential disease-related efficacy events meet the pre-specified clinical criteria defined in the Adjudication Committee charter. The definition of MI, for the purposes of adjudication will conform to the [Third Universal Definition of Myocardial Infarction](#). Other endpoint definitions will be based upon the [Standardized Definitions for Cardiovascular and Stroke End Point Events in Clinical Trials](#).

Clinical endpoints defined as primary or secondary efficacy parameters will be assessed beginning with the day of randomization. All potential disease-related efficacy endpoints occurring after randomization, through study completion/end of study visit, should be reported as an adverse event and submitted for adjudication, whether or not the subject is on double-blind investigational product.

After discontinuation of the bococizumab clinical development program, the sites were instructed to only forward those events occurring on or before 01 November 2016 for adjudication.

Only data from central laboratories will be used to assess the secondary circulating biomarker endpoints.

Changes from baseline will be calculated as the post-baseline value minus the baseline value.

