6.1.3. Other Secondary Endpoints

Other clinical secondary endpoints are *[t]he times from randomization to the first adjudicated and confirmed occurrence of the endpoints below (as defined in [Appendix 1.2](#)):*

- *A composite endpoint of CV death, non-fatal MI, non-fatal stroke, and hospitalization for unstable angina;*
- *CV death;*
- *Any MI (fatal and non-fatal);*
- *Fatal MI;*
- *Non-fatal MI;*
- *Any stroke (fatal and non-fatal);*
- *Any stroke (fatal and non-fatal), of any etiology;*

- *Fatal stroke;*
- *Non-fatal stroke;*
- *Hospitalization for unstable angina;*
- *Hospitalization for congestive heart failure (CHF);*
- *Any coronary revascularization procedure;*
- *CABG;*
- *PCI;*
- *Any arterial revascularizations;*
- *All-cause death.*

Circulating biomarker endpoints are secondary efficacy endpoints and include the lipid and inflammatory parameters listed below. Lipid parameters will be evaluated as percent change from baseline. In addition, LDL-C (direct and Friedewald) will be evaluated as nominal change from baseline. The inflammatory parameter, hs-CRP, will be evaluated as the percent change from baseline.

The sponsor, investigators and clinical staff and the subject will remain blinded to all circulating efficacy biomarker laboratory findings. Once all subjects have completed participation and the study is unblinded, results of the fasting lipid tests for each study participant will be sent to the investigator.

Investigators should inform the study subject's primary care physician (PCP) of the study design and the importance of maintaining the blind for lipid laboratory results. If possible, PCPs should refrain from measuring lipids while the subject is a participant in the study, if possible, but if measurement is necessary, they should refrain from informing the subject of the results. Subjects will be provided an information card to give to a health provider, when being seen for medical care or when undergoing phlebotomy that is not study related. The information card will explain the nature of the subject's participation in the study and that lipid and other biomarker data is being reviewed, to maintain the safety of the subject during the conduct of the trial.

Baseline will be calculated as the mean of the last two non-missing values prior to and including the randomization date.

Non-fasted as well as fasted measurements will be used in all summaries, analyses, and plots.

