8.2.2. Analysis of Secondary Endpoints

The secondary endpoints for clinical outcomes include the times from randomization to the first occurrence of the adjudicated and confirmed clinical endpoints described below. Time to each of these endpoints will be tested in the FAS with a log rank test stratified by geographic region and LDL-C at the pre-screening visit (<100 mg/dL, ≥100 mg/dL). For the key secondary endpoints, a fixed sequence testing procedure using the sequence indicated in [Section 4.2](#) will be used with a two-sided $\alpha=0.049$. For other secondary endpoints, and for analyses of the key secondary endpoints other than the log rank test, a two-sided $\alpha=0.05$ will be used. A Cox proportional hazards regression model for each endpoint will be fit with treatment group as a covariate and geographic region and LDL-C at the pre-screening visit (<100 mg/dL, ≥100 mg/dL) as stratification factors. If the model fitting fails to converge, LDL-C at pre-screening will be removed as a stratification factor. The hazard ratio, and a 95% confidence interval will be reported. The goodness of fit of the Cox proportional hazards regression model for the composite endpoint of cardiovascular death, non-fatal MI or non-fatal stroke will be assessed by visual inspection of Arjas plots. For the key secondary composite endpoint of cardiovascular death, non-fatal MI or non-fatal stroke, and for all-cause death, Kaplan-Meier estimates of time to first event will be plotted.

The reasons for censoring the key secondary composite endpoint of cardiovascular death, non-fatal MI and non-fatal stroke will be summarized by treatment group.

Key secondary endpoints

The key secondary endpoints (as defined in [Appendix 1.2](#)) are the times from randomization to the first adjudicated and confirmed occurrence of:

- A composite endpoint of CV death, non-fatal MI, and non-fatal stroke;
- A composite endpoint of all-cause death, non-fatal MI, and non-fatal stroke, and hospitalization for unstable angina needing urgent revascularization;
- A composite endpoint of all-cause death, non-fatal MI and non-fatal stroke;
- Hospitalization for unstable angina needing urgent revascularization.

Other secondary clinical endpoints

Other clinical secondary endpoints (as defined in [Appendix 1.2](#)) are the times from randomization to first adjudicated and confirmed occurrence of:

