- A composite endpoint of CV death, non-fatal MI, non-fatal stroke, and hospitalization for unstable angina;
- CV death;
- Any MI (fatal and non-fatal);

- Fatal MI;
- Non-fatal MI;
- Any stroke (fatal and non-fatal);
- Any stroke (fatal and non-fatal) of any etiology;
- Fatal stroke;
- Non-fatal stroke;
- Hospitalization for unstable angina;
- Hospitalization for congestive heart failure (CHF);
- Any coronary revascularization procedure;
- CABG;
- PCI;
- Any arterial revascularizations;
- All-cause death.

Adjudicated and confirmed causes of all-cause death will be tabulated by treatment group in the FAS. The tabulation will include the event rates and 95% confidence intervals. Causes of all-cause death will be classified according to the Adjudication Committee Charter.

The number and percent of the component that occurs first for the key secondary composite endpoints of cardiovascular death, non-fatal MI or non-fatal stroke will be summarized by treatment group.

Investigator reported potential secondary endpoint events will be listed.

Circulating biomarker secondary endpoints

Percent changes from baseline in all lipid endpoints and hs-CRP and nominal changes from baseline in LDL-C will be analyzed using a mixed model repeated measures (MMRM) model with fixed effects for treatment (categorical variable), scheduled visit time point (categorical variable), baseline value (continuous variable), interaction between baseline value and scheduled visit time point, interaction between treatment and scheduled visit time point, and geographic region (categorical variable) and LDL-C at the pre-screening visit (<100 mg/dL, ≥100 mg/dL). Observations will be assigned to visits using the analysis windows in [Table 3](#).

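### As written, the final all-cause-death analyses censor a known but unconfirmed death and give no date to an undated one, whereas the DMC test of the same endpoint counts both

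*SAP*

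**What the plan says.** **Final analysis, event.** SAP Section 6.1.3 defines the other clinical secondary endpoints, with all-cause death last in the list, as the "times from randomization to the first adjudicated and confirmed occurrence of the endpoints below". SAP Section 8.2.2 repeats that these endpoints "are the times from randomization to first adjudicated and confirmed occurrence of" the listed items, and Protocol Section 9.2.2.1.2 agrees: they "are the times from randomization to the first adjudicated and confirmed occurrence of" the same list. SAP Section 6.1.2 puts the same condition on the key secondary endpoints. The second and third of these contain all-cause death. All-cause death is also modelled in the Safety Analysis Set (SAP Section 8.1.1.1; Protocol Section 9.4).

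**Final analysis, censoring.** SAP Section 7 censors a subject with no primary-endpoint component at the earlier of last contact and 01November2016. It then adds: "The date of last contact is defined as the date of death, if the date is not missing". If the date is missing, the latest of several contact dates is used. The section extends this rule to all other clinical endpoints.

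**DMC test.** SAP Section 3 says: "The analysis will be based on a log-rank test of all-cause death, from all data sources". Missing death dates are imputed from the date of last contact. Protocol Appendix 5 gives the same rule.

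**Adjudication.** All-cause death is among the categories the Adjudication Committee reviews (SAP Section 6.1). After the programme stopped, "the sites were instructed to only forward those events occurring on or before 01 November 2016 for adjudication".

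**The concern.** Ending follow-up at a non-cardiovascular death is proper for the primary endpoint. The same rule does not fit all-cause death, where death is the event. A subject known to have died, but whose death was not confirmed by the committee, would leave the risk set as event-free on the day of the event. SAP Section 8.1.1.1 states that the log rank, Cox and Kaplan-Meier methods all assume censoring independent of the hazard. This censoring is not.

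The protocol looks for deaths by routes that may produce little for a committee to review. Withdrawn subjects agree to supply vital status (Section 3.3.4), public registries may be searched (Section 6.5.2), and vital status is required for every randomized subject (Section 7). Adjudication rests on a dossier of medical records (Sections 7 and 7.1.1).

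At stake are the death rates in the FAS and SAS, two key secondary endpoints tested at 0.049, and agreement between the final death count and the count the DMC tested. The planned censoring checks would not show the problem. Multiple imputation covers only the primary endpoint and only surviving subjects. Reasons for censoring are summarised only for the primary endpoint and the first key secondary composite (SAP Sections 8.1.1.1, 8.2.1 and 8.2.2).

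**Working it through.** **1. The plan's own figure.** The alpha allocated to the primary endpoint and to DMC monitoring of death (SAP Section 3) is 0.049 + 0.001 = 0.050, as stated. An interim test on a broader set of deaths still spends at most 0.001, so this figure does not change.

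**2. Tracing each kind of death through the rules.**

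| Death | Final all-cause-death analysis | DMC test |
|---|---|---|
| Confirmed, dated on or before 01November2016 | Event on that date | Event |
| Known, not confirmed, dated on or before 01November2016 | Censored on the date of death | Event |
| Confirmed, no date | No event date stated | Event, dated from last contact |
| Known, not confirmed, no date | Censored at the fallback contact date or 01November2016, whichever is earlier | Event, dated from last contact |
| Dated after 01November2016 | Censored at 01November2016 | Not at issue here |

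Rows 2 to 4 are the gap. The last row is ordinary administrative censoring. In key secondary endpoints 2 and 3 the gap matters only when the death would be the subject's first component.

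**3. Effect on rates.** A subject censored on the date of death contributes the same time at risk T as one counted as an event on that date. If a fraction f of D dated deaths is not counted, the rate becomes D(1 − f)/T, which is understated by exactly f. If f is equal in the two arms, it cancels from the rate ratio. If it differs, the ratio is multiplied by (1 − f₁)/(1 − f₀), where 1 and 0 denote bococizumab and placebo.

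**4. Scale, under assumptions.** The documents give neither f nor the expected number of deaths. I take f = 2%, 5% and 10%, and D = 200 and 400. Both values of D are rows of SAP Table 1, which illustrates numbers of deaths and does not forecast them. I use a hazard ratio of 0.8, two-sided alpha 0.05 and equal f in both arms. The formula is power = Φ(|ln 0.8| × √D / 2 − 1.96). As a check, D = 844 gives 90.0%, matching the protocol's approximately 90%.

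| Known deaths | Counted at f = 0 / 2% / 5% / 10% | Power |
|---|---|---|
| 200 | 200 / 196 / 190 / 180 | 35.1% / 34.5% / 33.6% / 32.2% |
| 400 | 400 / 392 / 380 / 360 | 60.7% / 59.8% / 58.5% / 56.2% |

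At 200 deaths, 200 × 2% = 4 and 200 × 10% = 20 deaths would be analysed as event-free. The largest power loss is 35.1 − 32.2 = 2.9 points at 200 deaths and 60.7 − 56.2 = 4.5 points at 400.

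**The case against.** The strongest reply is that the affected group may be nearly empty. All-cause death is adjudicated as its own category, every potential endpoint after randomization is sent for review whether or not the subject is on drug, sites must try to obtain the date and cause of death, and death certificate information is acceptable documentation. What confirmation requires is set in the Adjudication Committee Charter, which is not among the documents. SAP Section 8.2.2 says "Adjudicated and confirmed causes of all-cause death will be tabulated by treatment group in the FAS", with causes classified under the Charter. If the Charter confirms the fact of death separately from its cause, few or no deaths would be lost. This stands as a limit on size. It does not remove the gap, because nothing in the protocol or SAP says that an unconfirmed death counts.

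It is also fair that interim safety monitoring has to use all sources while adjudication is under way. A difference between interim and final data is therefore not a fault in itself. What is missing is a rule for the final count.

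A reader might infer that the SAP forbids imputing a death date, from this sentence in Section 7: "For all other efficacy and safety endpoints, missing values will not be imputed; missing values will remain missing". The word *other* defeats that reading. Clinical endpoints are dealt with earlier in the section, so the SAP is silent on undated deaths and does not prohibit imputation.

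**Conclusion.** The point holds as a gap in the event definition. The final rules would censor a known but unconfirmed death on its own date (or at 01November2016 if earlier), and they give an undated death no event date. The DMC rules for the same endpoint do neither. The gap reaches all-cause death in the FAS and SAS and key secondary endpoints 2 and 3. It does not touch the primary endpoint or the first key secondary composite, where death counts only if its cause is adjudicated as cardiovascular.

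The size cannot be derived from the documents and may be small. The figures of 4 to 20 deaths and power losses of up to 4.5 points rest wholly on the assumed fractions and death counts.

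Two stronger readings are not supported. A reader might infer that the hazard ratio is biased, but that needs confirmation to fail at different rates in the two arms. Adjudication is blinded and independent, and nothing in the documents points to a difference. A reader might also infer that Type 1 error control is damaged, but the 0.049 and 0.001 allocation is unaffected. The reason to act is that censoring at death breaks the stated assumption of independent censoring and that the repair is nearly free.

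**What to change.** In SAP Sections 6.1.2, 6.1.3, 7 and 8.2.2:

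- State that any death on or before 01November2016 known from any source is an event for all-cause death (FAS and SAS) and within key secondary endpoints 2 and 3.
- Use adjudication only to classify the cause of death.
- Date a death with a missing date by the last-contact rule already used for the DMC test.
- Record that this departs from Protocol Sections 2.2.2, 2.2.3 and 9.2.2.1. Protocol Section 9 lets the SAP modify the planned analyses and requires an amendment only for major changes to the primary endpoint or its analysis.

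The cost is a few sentences and a small change to the derivation. The downside is that a few deaths without cause documents enter the count, and an undated death carries an approximate date.
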